4.3. Exclusion Criteria

Participants who meet *any* of the following exclusion criteria at screening and randomization are not eligible to be enrolled in this study:

- 1) Received any investigational drug, RDV, or other antiviral treatment for COVID-19
- 2) ALT or AST $> 5 \times$ ULN
- 3) IMV, noninvasive mechanical ventilation, ECMO, or RRT for AKI
- 4) Positive serum pregnancy test at screening for women of childbearing potential or currently breastfeeding
- 5) Known hypersensitivity to the investigational drug, metabolites, or formulation SBECD

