6.2. Pretreatment Assessments

6.2.1. Screening Visit

Participants will be screened within 2 days before randomization to determine eligibility for participation in the study. The following will be performed and documented at screening:

- Obtain written informed consent (participant \geq 18 years of age) or assent from parent or legal guardian (participants $<$ 18 years of age, where locally and nationally approved)
- Determine eligibility requirements as specified in the inclusion and exclusion criteria
- Focused medical history will include date of first symptoms, overall symptoms, exposure source, demographics, baseline characteristics, concomitant medications, kidney or other transplant history, and allergies
- Complete physical examination, including vital signs (heart rate, temperature, blood pressure), actual body weight, and height
- Documentation of respiratory status:
 - Respiratory rate
 - Oxygenation: oxygen saturation (SpO₂), room air, low-flow O₂, high-flow O₂

CC

- Documentation of SARS-CoV-2 infection by PCR via 1 validated assay at a local laboratory, if not performed within the last 4 calendar days
- Document COVID-19 vaccine status (Note: It should be documented whether participant is fully or partially vaccinated, including any booster[s] received, if applicable.)
- Record the 8-point ordinal scale (see Section 6.9)
- Record any SAEs and all AEs related to protocol-mandated procedures occurring after signing of the informed consent (or assent) form
- IMV (yes/no; if yes, provide date when mechanical ventilation was started)
- RRT assessment
- If available, up to 3 SCr values prior to COVID-19 illness (eg, within the previous 6 months)
- Counsel participants of childbearing potential to use adequate birth control methods required during the trial to avoid pregnancy. See Appendix 4
- Laboratory evaluations: The following tests will be performed at screening. Results from within 48 hours prior to screening are acceptable; the entire panel of tests should be performed for all study participants if not done in the preceding 48 hours (see Section 6.5):
 - Chemistry, hematology, SCr, and coagulation
 - Urinalysis (participants who are oliguric are not required to provide a urine sample)
 - Pregnancy test (serum, for females of childbearing potential)

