7.2. Laboratory Evaluations

Laboratory data collected during the study will be analyzed and summarized using both quantitative and qualitative methods. Summaries of laboratory data will be provided for the Safety Analysis Set and will include data collected up to the last dose of study drug plus 30 days. The analysis will be based on values reported in conventional units. When values are below or above the LOQ, they will be listed as such, and the closest imputed value will be used for the purpose of calculating summary statistics as specified in Section 3.7.

Because RRT may significantly impact certain lab values such as SCr and BUN, a sensitivity analysis will be conducted, in which records and/or participants may be excluded from analysis as follows:

- SCr and BUN will only be analyzed for participants who are not on RRT at baseline. If RRT is used during the study, any records from RRT start to end + 3 days will be excluded from analysis.

RRT started within 3 days before first dose is considered RRT at baseline.

Anticoagulation medications can impact coagulation lab parameters, such as aPTT, PT, and INR. Sensitivity analysis will be conducted for coagulation lab parameters. Any coagulation lab records under the influence of these medications will be excluded from analysis. For anticoagulation medications in the Warfarin class, coagulation lab records with a date in between the start and 5 + the stop date of the medication will be excluded; for other anticoagulation medications, records with a date in between the start and 1 + the stop date of the medication will be excluded.

A by-participant listing for laboratory test results will be provided by participant ID number and visit in chronological order for hematology, coagulation, serum chemistry, CCI [REDACTED] Values falling outside of the relevant reference range and/or having a severity grade of 1 or higher on the DAIDS Grading Scale (see Section 7.2.2) will be flagged in the data listings, as appropriate.

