- If the end date is incomplete but the month and year (or year alone) of the end date is before the month and year (or year alone) of the first dosing date of study drug, the event will not be included.

A variable for each of the risk factors will be added to raw Medical History and Adverse Events datasets. A medical history or an AE record will be flagged for a risk factor if its MedDRA PT is included in the prespecified PT list for the corresponding disease of interest, which includes all PTs from the narrow or broad search of the following SMQs under MedDRA 25.0 provided by

Gilead GLPS and reviewed by Gilead medical monitors.

Disease of Interest	SMQ or MedDRA HLT Source
Chronic lung disease	HLT of bronchospasm and obstruction
Hypertension	Hypertension (SMQ)
Cardiovascular or cerebrovascular disease	Ischaemic central nervous system vascular conditions (SMQ); Myocardial infarction (SMQ); Other ischaemic heart disease (SMQ)
Diabetes mellitus	Hyperglycaemia/new onset diabetes Mellitus (SMQ)
Immunocompromised state	HLGT for “Immunodeficiency syndromes”
Chronic liver disease	search name “Chronic liver disease excluding transient_acute events and nonspecific signs_symptoms”
Current cancer	Malignancies (SMQ)

10) Details on SCr and BUN record exclusion for sensitivity analysis

SCr and BUN will only be analyzed for participants who are not on RRT at baseline.

RRT at baseline:

RRT started within 3 days of first dose is considered RRT at baseline. An RRT record with an end date prior to the first dose date - 3 days (or 72 hours if time available) or a start date/time after the first dose date/time will not be considered a baseline RRT record; otherwise, the record will be considered baseline.

SCr/BUN record exclusion (for participants who are not on RRT at baseline):

Any SCr/BUN records from an RRT start to end + 3 days will be excluded from analysis.

If both date and time are collected for RRT and labs, only date will be used, with 1 exception below:

If an SCr/BUN record is collected on the first dose date and prior to first dose time, and the participant's first RRT starts on the first dose date but after first dose time, then this lab record will not be excluded.

RRT date:

A missing end date of a hemodialysis record will be imputed using the hemodialysis start date.

If an end date is missing for a CVVH record:

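### RRT at baseline for the creatinine/BUN sensitivity analysis is set from dated RRT records alone, without the ESKD status already collected, so some chronic-dialysis participants can be left in

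*SAP*

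**What the plan says.** SAP 7.2 notes that RRT can distort creatinine and BUN, and so "a sensitivity analysis will be conducted, in which records and/or participants may be excluded from analysis as follows". The first condition is that "SCr and BUN will only be analyzed for participants who are not on RRT at baseline". For those participants, values are also dropped from the start of each RRT record until 3 days after its end.

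Baseline RRT is worded in three ways:

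- SAP 7.2: "RRT started within 3 days before first dose is considered RRT at baseline".
- Appendix 2 item 10, opening sentence: "RRT started within 3 days of first dose is considered RRT at baseline".
- Appendix 2 item 10, operative sentence: this disqualifies "An RRT record with an end date prior to the first dose date - 3 days (or 72 hours if time available"), and any record that starts after first dose. Every other record counts as baseline.

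Item 10 adds that "A missing end date of a hemodialysis record will be imputed using the hemodialysis start date", with no exception for ongoing maintenance dialysis. A CVVH record that is open and is the last or only one is treated differently: unless the participant died, it stays open and all later SCr and BUN values are dropped.

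Protocol 4.3 excludes "IMV, noninvasive mechanical ventilation, ECMO, or RRT for AKI", so participants on RRT at baseline should essentially be the ESKD stratum. ESKD status at Screening is on the Enrollment CRF (item 15). The SAP uses ESKD status for kidney disease status (item 15), RRT-free days (6.2.1) and peak SCr (item 17), but not in this rule.

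**The concern.** The analysis is meant to show creatinine and BUN free of the effect of dialysis. The group to be removed is known from a flag, yet the SAP identifies it from records that may be incomplete or open-ended. RRT is assessed from screening (Protocol Appendix 3), and "Participants will be screened within 2 days before randomization to determine eligibility for participation in the study", which is shorter than the 3-day look-back. A session on Day 1 follows the dose (Protocol 5.3), so it cannot count as baseline. A participant on maintenance dialysis may then have no qualifying record. At stake is whether this supporting view of renal laboratory safety contains only the participants it is meant to contain.

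**Working it through.** The plan states no figure for this rule, so there is none to reproduce. The check applies item 10 by calendar date.

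**Inputs.** First dose is day 0 (Study Day 1). A record has start s and end e.

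- Baseline record: e ≥ −3 and s not after first dose (item 10).
- Missing hemodialysis end: e = s (item 10).
- Lab value on day d dropped if s ≤ d ≤ e + 3 (SAP 7.2, item 10).
- SCr daily on Days 1 to 29, so d = 0 to 28, or 29 days if still in hospital (Protocol 6.5).
- A session on day 0 starts after the dose (Protocol 5.3).
- Assumptions: the layout of the RRT form is not given, so several patterns are tried. Session gaps are 2, 2 and 3 days (thrice weekly), 3 and 4 (twice weekly), or 7 (once weekly), over all 7 positions of first dose in the week.

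**One open record.** Take s = −730 (assumed), end missing. Then e = −730 < −3, so the participant is not on RRT at baseline. The filter covers only days −730 to −727, so 29 of 29 SCr days are kept, provided that no in-study sessions are also entered. Had the record stayed open, it would be baseline and 0 days would be kept.

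**Thrice weekly, by session.** The longest gap is 3 days, so with complete records the last pre-dose session is on day −1, −2 or −3 and always qualifies. If pre-dose sessions are missing, the second filter still works: each session removes 4 calendar days (s to s + 3) and the next comes within 3. Nothing is kept after the first recorded in-study session. If records start only at first dose, that session falls on day 0 or 1 (each gap of 2) or day 0, 1 or 2 (the gap of 3), so 0 to 2 days are kept.

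**Once weekly, by session.** The last pre-dose session is on day −4, −5, −6 or −7 in 4 of 7 positions, so the participant is not baseline. Each session removes 4 of 7 days and leaves 3. Four weeks give 4 × 3 = 12, and the 29th day adds 0 or 1, so 12 to 13 days are kept.

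| Recording pattern | Classed as not on RRT | SCr days kept when misclassified |
|---|---|---|
| One open record, no sessions | yes | 29 |
| 3/week, all sessions | 0 of 7 | none |
| 3/week, from 2 days before first dose | 1 of 7 | 0 |
| 3/week, last pre-dose session missed | 5 of 7 | 0–1 |
| 3/week, from first dose only | 7 of 7 | 0–2 |
| 2/week, all sessions | 1 of 7 | 0 |
| 2/week, from first dose only | 7 of 7 | 0–3 |
| 1/week, all sessions | 4 of 7 | 12–13 |
| 1/week, from first dose only | 7 of 7 | 12–15 |

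Two details do not change the picture. If the first recorded RRT is a Day 1 session after dosing, item 10 keeps that day's predose value, so a row showing 0 days may still contribute a baseline value. If times are used, a thrice-weekly session 3 calendar days before dosing may have ended more than 72 hours earlier, which affects 1 of the 7 positions. The next session is then on Day 1, the record filter works by date, and 0 post-baseline days are kept.

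**The case against.** The strongest reply is that item 10 reads as if hemodialysis is entered by session. Setting a missing end to the start date suits a session, and the continuous modality has its own open-ended rule. The reference to records ending more than 3 days before first dose also suggests that sessions before screening are expected. The SAP says it is based on the eCRF. On complete thrice-weekly records the rule makes no error. This stands, and it is why the likely effect is small.

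A reader might infer more, and the documents do not support it:

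- **That up to 20% of participants enter with all their values**, from the cap on ESKD in Protocol 5.1.1. This needs every such participant to be entered as one open-ended record, and the text of item 10 points the other way.
- **That dialysis swings could mimic or hide a drug effect.** Randomization is stratified by ESKD requiring chronic dialysis, so misclassification should be roughly balanced. At thrice-weekly frequency the second filter removes almost all values between sessions.
- **That the RRT-at-baseline row in SAP 5.2 will disagree with the ESKD stratum.** Section 5.2 does not cite item 10, whose title limits it to the SCr/BUN sensitivity analysis.
- **That SAP 7.2 leaves out all long-standing dialysis.** Item 10 gives the details, and its operative sentence works on the record's end date. The wording on when RRT started needs aligning; it is not a separate error.

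The main laboratory summaries, the listings of renal adverse events and RRT, and peak SCr do not depend on this rule.

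**Conclusion.** The gap is real and minor. Followed as written, the rule can keep in some participants whom the analysis is designed to leave out, although a variable that identifies them is already collected. On session-level records at three sessions a week, the error per misclassified participant is usually 0 to 2 lab days. It is 12 to 13 for once-weekly dialysis (up to 15 if nothing before first dose is recorded), and all values only for a single open-ended record. These counts rest on the assumed schedules and recording patterns. The number of participants affected cannot be derived from the documents. No efficacy endpoint or alpha is involved.

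**What to change.** In SAP 7.2 and Appendix 2 item 10, define RRT at baseline as either ESKD requiring chronic dialysis = Yes at Screening (Enrollment CRF), or an RRT record meeting the item 10 rule. Exclude all such participants from the SCr/BUN sensitivity analysis. In both places, replace the wording on RRT started within 3 days with the operative record-level rule.

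Leave the hemodialysis end-date imputation unchanged. Restricting it to records that start on or after first dose would leave earlier records with a missing end date without any rule. If these were read as open, an isolated old session could wrongly exclude a participant without ESKD.

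The cost is a sentence or two of SAP text and one added condition in the program. It uses a collected variable, works however hemodialysis is recorded, and removes nobody the analysis means to keep. It assumes that the ESKD field on the Enrollment CRF means ESKD requiring chronic dialysis, which should be confirmed.

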2.2. DMC Analyses

Two formal DMC meetings were planned for this study and were specified in protocol Sections 8.2 and 8.10. The first meeting has occurred and was conducted after the first 100 participants completed the Day 29 assessment. The purpose of this meeting was to review safety data, including renal and hepatic toxicity. The second meeting was planned after 50% of participants completed the Day 29 assessment. The purpose of this meeting was to review safety and provide a formal evaluation of futility and efficacy. However, this analysis was not performed due to the stop of study enrollment prior to reaching 50% of planned enrollment.

In addition to the above mentioned 2 formal DMC analyses, the DMC was provided with blinded safety listings including Grade 3 or higher AEs and SAEs every week for the first 2 weeks after the first participant was enrolled followed by every 2 weeks thereafter.

All details on DMC analyses are documented in the approved DMC charter.

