6.1.3. Primary Analysis of the Primary Efficacy Endpoint

The primary endpoint will be analyzed using a stratified log-rank test stratified by the randomization strata. P value and the proportion of all-cause mortality or IMV at Day 29 from Kaplan-Meier estimate will be provided.

The hazard ratio and 95% confidence interval (CI) will be estimated using a Cox model with stratification factors as covariates.

Participants with missing outcomes for the primary endpoint due to premature discontinuation of the study on or prior to Day 29 will be censored at the last study day.

Additionally, the difference in proportions of all-cause mortality or IMV at Day 29 between treatment groups and the 95% CI for the difference will be provided based on the stratum-adjusted Mantel-Haenszel (MH) proportion as described in {Koch 1989} in [Appendix 2](#).

The FAS will be the primary analysis set for efficacy endpoint evaluation.

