6.2.1. Analysis of Secondary Efficacy Endpoints

The key α -controlled secondary endpoint of all-cause mortality through Day 29 will be analyzed in a similar manner to the primary endpoint.

Initiation of IMV through Day 29 and time to recovery through Day 29 will also be analyzed in a similar manner to the primary endpoint except that a competing risk analysis approach will be used with death as the competing risk.

For analysis on time to recovery through Day 29, two sets of analyses will be conducted:

(1) Time to recovery through Day 29, in which the first recovery without further worsening in the ordinal scale score (ie, a score of > 4) by Day 29 will be considered an event; (2) Time to recovery through Day 29, in which the first recovery (regardless of further worsening or not) will be considered an event.

The clinical status assessed by the 8-point ordinal scale at Day 15 and Day 29 will be analyzed using a proportional odds model including treatment as the independent variable. Two models will be explored; one with baseline score as a continuous covariate and one without baseline score as a covariate. The odds ratio and 95% CI will be provided. The percentage of participants in each category will be summarized by treatment group. The assumption of odds proportionality will be assessed using a score test and reported. Clinical status by study day and change from baseline up to Day 29 will also be summarized by treatment group.

For participants without ESKD at baseline, the number of RRT-free days will be calculated between date of first dose and Day 29. The number of RRT-free days will be calculated as the number of full days from Day 1 to Day 29 that the participant was alive and did not receive RRT. The number of RRT-free days will be summarized by treatment group, and compared between treatment groups using Wilcoxon rank sum test.

The proportion of participants with recovery through Day 29 will be summarized by treatment group, and compared between treatment groups using the CMH test stratified by randomization strata. Similar for time to recovery analysis, two sets of analyses will be conducted: (1) The proportion of participants with recovery through Day 29, in which recoveries without further worsening by Day 29 is considered; (2) The proportion of participants with recovery through Day 29, in which recoveries regardless of worsening status by Day 29 is considered.

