label Estimate ="Percentage Difference"
LowerCL = "95% Lower Confidence Limit"
UpperCL = "95% Upper Confidence Limit"
A1 = "Percentage of Success in Treat-A"
B1 = "Percentage of Success in Treat-B";
Estimate=100*_RDIF1_;
LowerCL = 100*XL_RDIF1;
UpperCL = 100*XU_RDIF1;
A1 = 100*_RSK11_;
B1 = 100*_RSK21_;
ocharc1 = right(compress(put(Estimate,8.1)) || '% (' || compress(put(LowerCL,8.1)) || '%
to ' || compress(put(UpperCL,8.1)) || '%)');
run;
```

13) Difference in proportions between treatment groups adjusted by stratum

The 95% confidence interval for difference in between treatment groups will be calculated based on the stratum-adjusted Mantel-Haenszel (MH) proportion as described as follows {Koch 1989}, where the stratification factors include ESKD (Yes, No), High-flow oxygen requirement (Yes, No), and region (US, ex-US):

$$P_1 - P_2 \pm Z_{(1-\alpha/2)} * SE(P_1 - P_2),$$

where

- $(P_1 - P_2) = \frac{\sum w_h d_h}{\sum w_h}$, is the stratum-adjusted MH proportion difference, where $d_h = p_{1h} - p_{2h}$ is the difference in the proportions of Treatment Groups 1 and 2 in stratum h .
- $w_h = \frac{n_{1h} n_{2h}}{n_{1h} + n_{2h}}$, is the weight based on the harmonic mean of sample size per treatment group for each stratum where n_{1h} and n_{2h} are the sample sizes of the Treatment Groups 1 and 2 in stratum h .
- $SE(P_1 - P_2) = \sqrt{\frac{\sum \left[\frac{p_{1h}^* (1 - p_{1h}^*)}{n_{1h} - 1} + \frac{p_{2h}^* (1 - p_{2h}^*)}{n_{2h} - 1} \right]}{(\sum w_h)^2}}$, where $p_{1h}^* = \frac{m_{1h} + 0.5}{n_{1h} + 1}$ and $p_{2h}^* = \frac{m_{2h} + 0.5}{n_{2h} + 1}$. m_{1h} and m_{2h} are the number of participants with event interest at Day 29 in Treatment Groups 1 and 2 in stratum h .
- $\alpha = 0.05$ for this study
- $Z_{(1-\alpha/2)} = Z_{0.975} = 1.96$ is the 97.5th percentile of the normal distribution

Note that if the computed lower confidence bound is less than -1, the lower bound is defined as -1. If the computed upper confidence bound is greater than 1, the upper bound is defined as 1.

To facilitate SAS macro use, a single stratum variable could be defined as:

ESKD requiring chronic dialysis	High-flow oxygen requirement	Region	Stratum
Yes	No	US	1
Yes	No	ex-US	2
Yes	Yes	US	3
Yes	Yes	ex-US	4
No	No	US	5
No	No	ex-US	6
No	Yes	US	7
No	Yes	ex-US	8

14) Clarification for SE(P1-P2) Calculation in 13).

- if n_{1h} or $n_{2h} > 1$ the denominator $n_{1h} - 1$ or $n_{2h} - 1$ was calculated as indicated in the formula;

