- if n_{1h} or $n_{2h} = 1$, the corresponding n_{1h} or n_{2h} will be adjusted to 2, then corresponding denominator $[(n_{1h} - 1)$ or $(n_{2h} - 1)]$ is 1;
- if n_{1h} or $n_{2h} = 0$, then the corresponding stratum will be ignored, will not be included in the calculation, thus the proportion difference and 95% CI are still calculable.

15) Kidney disease status definition

Kidney disease data at baseline are collected in this study, including: history of CKD and ongoing AKI from the Medical History CRF form, ESKD status at Screening from the ENROLLMENT CRF form, and renal transplant history from the Transplant History CRF form.

Expected data patterns are as follows (renal transplant history can be present or absent for any of these combinations):

	Ongoing AKI (from MH CRF question)	History of CKD (from MH CRF question)	ESKD status at Screening (from ENROLLMENT CRF)	Kidney Disease Status
1	Yes	Any	No	AKI
2	No	Yes	No	CKD
3	Any	Any	Yes	ESKD

Kidney disease status is defined as:

- AKI: the 1st row of the above table, ie, ongoing AKI with or without history of CKD
- CKD: the 2nd row of the above table, ie, history of CKD without ongoing AKI
- ESKD: the 3rd row of the above table.

16) For demographics tables, “Not Permitted” will be excluded from percentage for detailed race categories summary (ie, race categories collected on eCRF). For combined Race Category (e.g. Asian, White, Black, Other), “Not Permitted” is included in “Other” and “Other” will be included in the count of percentage.

17) For calculation of peak serum creatinine (SCr) through Day 29 (among those without ESKD at baseline), (1) baseline records will not be included; (2) Day 1 postdose is included in the calculation; (3) for multiple records within one day, the observed record with max SCr will be selected; (4) For multiple days has the same highest value, the earliest will be picked.

18) Death date imputation

For a partial death date where the year and month are available but the date is missing, the following imputation will be performed:

- If the latest clinical date (ie, the latest of study drug start dates and end dates, the in-person or phone visit dates, the vital sign and the laboratory collection dates, including the Day 60 phone follow-up visit date) falls into the same year/month of death, then this latest clinical date will be used to impute the date of death;

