The binary indicator variable (cnsr) with a value of 0 indicates the time to the event of interest is complete or 1 indicates the time to the event is censored.

26) Competing risk analysis

The following SAS code will be used to generate the cause-specific hazard ratio and 95% confidence intervals for the competing risk analysis:

```
proc phreg;
  class trt strat1 strat2 strat3;
  model aval* cnsr (1, 2) = trt strat1 strat2 strat3 / rl;
  hazardratio "Cause-specific hazard" trt;
run;
```

where $cnsr = 0$ if the participant had the event; $cnsr = 2$ if the participant died prior to having the event, and $cnsr = 1$ if the participant did not have the event and did not die.

SAS codes to obtain a cumulative incidence function plot and dataset for further processing for time to first event table:

```
proc lifetest outcif=outcif plots=cif;
  strata trt;
  time aval* cnsr (1) / failcode = 0; *Note: this produces data for the event of interest only;
run;
```

SAS code to obtain support tables:

```
proc univariate;
  by trt cnsr;
  var aval;
  output pctlpre=P_ min=min max=max pctlpts= 10, 25, 50, 75, 90;
run;
```

27) SAS code for stratified 2-sided Wilcoxon Rank sum test (stratified on baseline result)

```
proc freq;
  table base*trt*aval/cmh2 scores=modriddit;
run;
```

where BASE is the baseline value.

28) SAS code for ANCOVA:

```
ods output ParameterEstimates=out1 LSMeans=out2 LSMeansCL=out3
LSMeansDiffCL=out4;
```

```
proc glm data=dat1 plots=none;
  class trt;
  model DAVG = trt base / solution;
  lsmeans trt / stderr cl pdiff;
run;
ods output close; quit;
```

29) SAS code for CMH test and estimates with stratification factors adjustment:

```
proc freq data=dat1;  
  tables strat1*strat2*strat3*trt*Y/ list cmh;  
ods output cmh=cmhpval CommonRelRisks=risk;  
run;
```

30) Renal and hepatic adverse events include preferred terms from search term list 'Acute Renal Failure (SMQ)' and search term list 'Acute and non-infectious liver events' MedDRA 25.0.

31) Vital signs, and SCr collected after Day 29, PCR collected after day 44 will be assigned to "Post Day 29".

CCI [REDACTED]

33) For coagulation laboratory tests, both local and Covance lab records are collected in the data. In a visit where both Covance and local lab records are collected, Covance records will be picked over local lab records.

34) Reference ranges are based on Covance laboratory reference ranges.

35) COVID-19 medications include the following drugs:

Drug name
Chloroquine

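### As it reads, the standard error for the stratum-adjusted Day 29 risk difference omits the squared stratum weights, so its 95% CI would be too narrow if programmed literally

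*SAP*

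**What the plan says.** SAP 6.1.3 adds to the log-rank test and Cox model a difference in Day 29 proportions, for which "the 95% CI for the difference will be provided based on the stratum-adjusted Mantel-Haenszel (MH) proportion" as set out in Appendix 2. SAP 6.2.1 states that the key "secondary endpoint of all-cause mortality through Day 29 will be analyzed in a similar manner to the primary endpoint", so the same interval may also be reported for mortality.

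Appendix 2, item 13 specifies:

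- the estimate, Σw_h d_h / Σw_h, where d_h is the difference in proportions in stratum h;
- the weight, w_h = n1h·n2h/(n1h + n2h), which "is the weight based on the harmonic mean of sample size per treatment group for each stratum";
- the standard error, which reads "SE(P_1 - P_2) = \sqrt{\frac{\sum \left[\frac{p_{1h}^* (1 - p_{1h}^*)}{n_{1h} - 1} + \frac{p_{2h}^* (1 - p_{2h}^*)}{n_{2h} - 1} \right]}{(\sum w_h)^2", where p* adds 0.5 to the event count and 1 to the stratum size;
- eight strata, from ESKD, high-flow oxygen and region.

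Item 14 clarifies this SE. Where an arm has more than one participant in a stratum, the n − 1 denominator "was calculated as indicated in the formula". Where it has one, the denominator becomes 1. Strata with an empty arm are dropped, "thus the proportion difference and 95% CI are still calculable". Item 29, the SAS code for stratified estimates, requests "ods output cmh=cmhpval CommonRelRisks=risk": a CMH p-value and common relative risks. No code is printed for the SE in item 13.

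**The concern.** The point estimate is weighted by w_h, but the variance that reads in item 13 is not. Its denominator carries the squared sum of the weights, and its numerator has no matching w_h². Weights grow with stratum size, so the omission shrinks the SE at any realistic sample size.

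The interval is prespecified for the primary endpoint. Enrollment stopped below half of plan, so precision is limited. A falsely tight interval could exclude zero beside a non-significant stratified log-rank test and be read as support for an effect. Item 13 is the only printed specification a programmer has for this interval.

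**Working it through.** **Plan figures.** The SAP gives no numeric SE to reproduce. The planning risks were checked through the power statement in SAP 1.3. A placebo rate of 35% and HR 0.70 give an RDV rate of 1 − 0.65^0.70 = 26.0%. Expected events are 744 × 0.2603 + 372 × 0.35 = 323.9, and Schoenfeld power at two-sided 0.05 is 85.7%, against about 85% stated. This agrees, does not involve item 13, and supplies the risks used below.

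**Algebra.** Let v_h = p1h*(1 − p1h*)/(n1h − 1) + p2h*(1 − p2h*)/(n2h − 1), the bracketed term. For independent strata:

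- Var(Σw_h d_h / Σw_h) = Σw_h² v_h / (Σw_h)²
- as it reads: Σv_h / (Σw_h)²
- ratio of correct to as-read SE = √(Σw_h² v_h / Σv_h)

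**Two checks that need no assumed N or strata.**

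1. With one stratum the as-read SE equals the correct SE divided by w.
2. Item 13 relates w_h to the harmonic mean, but the harmonic mean itself is 2·n1h·n2h/(n1h + n2h) = 2w_h. Using 2w_h leaves the estimate unchanged and halves the as-read SE. A valid SE cannot depend on the scale of the weights.

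Numerically, for one stratum of 167 vs 83: w = 167 × 83/250 = 55.4 and v = 0.003944. The correct SE is √0.003944 = 0.0628. The as-read SE is 0.0628/55.4 = 0.0011, or 0.0006 with weight 2w.

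**Worked eight-stratum table (N = 240; sizes assumed, risks 26% vs 35%).**

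| RDV/placebo per stratum | Strata | w_h | v_h | w_h² v_h |
|---|---|---|---|---|
| 14/7 | 2 | 4.667 | 0.0542 | 1.180 |
| 2/1 | 2 | 0.667 | 0.4688 | 0.208 |
| 54/27 | 2 | 18.000 | 0.0125 | 4.044 |
| 10/5 | 2 | 3.333 | 0.0811 | 0.901 |
| Sum over 8 | | 53.33 | 1.233 | 12.665 |

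- As it reads: √1.233/53.33 = 0.0208; half-width 1.96 × 0.0208 = 4.1 points; CI −13.1% to −4.9%.
- With w_h²: √12.665/53.33 = 0.0667; half-width 13.1 points; CI −22.1% to +4.1%.
- Ratio 3.2. The two intervals disagree about zero.

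**Range of N.** SAP 2.2 reports that the first DMC meeting "was conducted after the first 100 participants completed the Day 29 assessment", and that enrollment stopped before 50% of plan. N is therefore at least 100 and below 1116/2 = 558.

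**Simulation.** Eight strata, 2:1 allocation in blocks of 3 per stratum or unblocked, item 14 rules, no dropout, 20,000 trials per scenario. There were 15 assumed mixes: ESKD 2–20% (the cap in Protocol 5.1.1 is 20%), high-flow 2–50%, US 5–95%. In total 15 × 2 × 3 × 20,000 = 1.8 million trials.

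| N | Median SE ratio over mixes | Smallest ratio in any trial | Coverage as it reads |
|---|---|---|---|
| 100 | 2.1–3.7 | 1.24 | roughly 43–68% |
| 250 | 3.6–5.3 | 2.40 | roughly 26–43% |
| 557 | 5.9–12.1 | 3.77 | roughly 13–26% |

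With w_h², coverage is 95–96%. With lower risks (15% vs 20%, a stand-in for mortality), as-read coverage is 48–74%, 29–48% and 14–29%, and the smallest ratio is 1.08. A separate fixed layout (ESKD 20%, high-flow 20%, US 50%; risks 26% vs 35%) gave 70% at N = 100, 32% at N = 300 and 15% at N = 557.

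**When the direction reverses.** This needs w_h below 1 in most strata. Eight strata of 1/1 give 0.433 as it reads against 0.217; eight of 2/1 give 0.303 against 0.202. Those are trials of 16 to 24 participants, below the minimum of 100.

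**The case against.** The strongest objection is that the symbol may have been lost when the PDF was read. Small symbols were misread elsewhere: in the study procedures table, the pregnancy test carries footnote h in Protocol Appendix 3 but g in SAP Appendix 1, and urinalysis is marked l in one and d in the other although its footnote is t. The surrounding text also points to the weighted form. A (Σw_h)² denominator makes sense only over a numerator in w_h², the point estimate is stated correctly, and item 13 cites a published method and mentions a SAS macro that is not shown. A typing or reading slip is more likely than an intended method. This stands, and it is why the conclusion is conditional. It does not show that the source page or the macro is right.

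The second objection is that the interval is supportive and the harm needs literal programming. That also stands and limits the severity. It does not remove the need for a check, because no printed item restores the weight.

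The third is that the size is loosely known. That is fair: the SE is too small by only about a factor of two at N = 100, and the coverage ranges are illustrative rather than bounds, as the 70% result at N = 100 shows.

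**Conclusion.** The concern holds as stated. The SE in item 13, as it reads, is not the SE of the estimator that item 13 defines. That follows from algebra alone. Programmed literally, it would make the CI in SAP 6.1.3 too narrow: by a factor of about 2 to 4 at N = 100 and about 6 to 12 at N = 557, with coverage far below 95%. These sizes rest on assumed stratum mixes, the planning risks and no dropout, because actual N and stratum counts are not in the documents. The direction was the same in every simulated trial with N of 100 or more.

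The claim covers the full FAS comparison for the primary endpoint, and mortality if the same interval is reported there. The stratified log-rank test, Cox hazard ratio, gatekeeping and power are untouched. Confidence is medium, because the source page has not been seen. It should be fixed, but it does not threaten the primary test.

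**What to change.** State the standard error in item 13 as

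SE = √{ Σ w_h² [ p1h*(1 − p1h*)/(n1h − 1) + p2h*(1 − p2h*)/(n2h − 1) ] / (Σw_h)² }

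and keep the 0.5 correction and the item 14 rules. Check the source page of the SAP and the SAS macro against this. A quick test of the macro is to double all weights and confirm that the SE does not change. If both already carry w_h², nothing needs to change.

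The cost is one term in one formula and one check of the macro. It needs no new data and does not alter the primary test.
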